15.3 Analysis of the Aim 2 Endpoints

Primary endpoints include the net change in perceived sexual health measured using the Patient-Reported Outcomes Measurement Information System (PROMIS) and perceived physical and mental health measured using the SF-12 Health Survey (SF-12).

- The PROMIS is a 96-item form developed by the NIH that measures 11 domains of biopsychosocial function and includes an assessment of sexual function measures (e.g., desire, frequency, fear, and pain) related to sexual intercourse.¹¹⁵
- The SF-12 assesses 6 domains: global health, physical functioning, physical roles, emotional functioning, emotional roles and pain interference using an algorithm¹¹⁸ based on answers to 12 physical and mental health-related questions.

Secondary endpoints include net changes in perceived mood and health using:

- Symptom Check List 27 (SCL-27), which measures a broad range of psychological symptoms (e.g., anxiety and depression) and has high reliability and strong correlations to pain.^{121,122}
- Pennebaker Index of Limbic Languidness (PILL), which is used to create a summary score of somatic symptoms (e.g., itchy eyes, dizziness). Symptom frequency is recorded on a five-point Likert scale ranging from “never” to “more than once a week”.¹⁰⁸
- Perceived stress scale (PSS), which is a 10-item scale that measures the impact of personal stress on thoughts and feelings.
- Sleep Scale, which is a 12-item scale that measures amount of sleep and ease/difficulty of initiating and maintaining sleep

Data Analysis. The two primary statistical questions for Aim 2 are: 2a) At baseline, do women with VBD-c exhibit worse perceived physical, mental, or sexual health than women with VBD-p? 2b) Considering physical, mental, or sexual health, is peripheral treatment with lidocaine/estradiol cream more effective than nortriptyline in VBD-p, and central treatment with nortriptyline more effective than lidocaine/estradiol cream in VBD-c?

To answer question 2a, we will fit three linear regression models with the dependent continuous variable being a variable for each of the 3 patient reported outcomes (SF12 physical health score, SF12 mental health score, and PROMIS sexual health score). VBD subtype will be the predictor of interest. Covariates will include age (continuous variable), race (coded as in model 1a), study site. Regression coefficient for VBD subtype will be tested for statistical significance using Bonferroni-corrected threshold alpha 0.0166 (corrected for 3 tests corresponding to 3 outcomes). Regression coefficient significance will suggest outcomes differ by VBD subtype.

To answer question 2b, three MMRM models analogous to model 2b will be fit, where Y is a continuous variable representing the primary outcomes measured at 16 weeks. Similar to 2b, we will jointly evaluate the significance of additional interaction terms using an F-test (“overall test”). Significant F-test will suggest that the effect of either nortriptyline or lidocaine/estradiol cream, or both, differ by VBD subtype. In this case, we will compare the LS means of the treatment differences in each treatment-VBD-subtype subgroup, after appropriate Bonferroni correction. Secondary outcomes will also include change in SCL-27 mood score, PILL somatization score, and PROMIS biopsychosocial trait scores from baseline to 16 weeks following treatment. Secondary outcomes also include change in patient-reported outcomes from baseline to the 8-week time point and change in pain scores and PPTs from the 16-week to the 24-week time point.

Expected Outcomes. **1)** For women with VBD-p, peripheral lidocaine/estradiol treatment will be more effective than placebo or nortriptyline in improving perceived physical, mental, and sexual health at 8 and 16 weeks. **2)** For women with VBD-c, centrally-targeted nortriptyline treatment will be more effective than placebo or lidocaine/estradiol in improving perceived physical, mental, and sexual health at 16 weeks. **3)** For women with VBD-c, combined peripheral and centrally-targeted treatments will be most effective in improving health at 16 weeks. **4)** The two VBD subtypes will exhibit differential responses to treatment withdrawal, such that women with VBD-c report decreases in perceived health from 16 to 24 weeks compared to women with VBD-p.

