4 AIMS AND HYPOTHESES

1. Determine the efficacy of peripheral, central, and combined treatments in alleviating pain among women with VBD-p and VBD-c. We hypothesize that women with VBD-p will preferentially respond to peripheral treatment, while those with VBD-c will preferentially respond to central or combined treatment. To test this hypothesis, we will measure pain in response to standardized tampon insertion with a numeric rating scale and self-reported pain on the McGill questionnaire at the first baseline clinic visit (0) and at 8, 16, and 24 weeks.

2. Determine the efficacy of peripheral, central, and combined treatments in improving patient reported outcomes among women with VBD-p and VBD-c. We hypothesize that women with VBD-c will exhibit more abnormalities in perceived physical, mental, and sexual health compared to those with VBD-p. We also hypothesize that women with VBD-c will demonstrate greater improvement in perceived health with central or combined therapy; while women with VBD-p will demonstrate greater improvement with peripheral treatment. To test these hypotheses, we will measure self-reported physical /mental health with the SF12 and sexual health with the PROMIS questionnaire administered at 0, 8, 16, and 24 weeks.

3. Determine the efficacy of peripheral, central, and combined treatments in normalizing cytokine and microRNA expression profiles in vaginal and blood tissues collected from women with VBD-p and VBD-c. We hypothesize that higher levels of inflammatory mediators in peripheral vaginal samples will be associated with VBD-p, while higher levels in circulating blood will be observed in women with VBD-c. We also hypothesize that peripheral treatment will resolve abnormalities in vaginal biomarkers, while central treatment will resolve abnormalities in blood biomarkers. Finally, we hypothesize that abnormalities in vaginal cytokine and miRNA biomarkers will predict a positive response to peripheral treatment, while abnormalities in blood biomarkers will predict a positive response to central or combined treatment. To test these hypotheses, we will use multiplex assays to measure cytokines and small RNA sequencing to measure miRNAs in samples collected at 0, 8, 16, and 24 weeks.

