To answer questions 1a and 1b, we will fit mixed model repeated measures (MMRM) models which account for missing data as an integral part of the analyses under the assumption of ignorable missing. To answer question 1a, the MMRM model includes longitudinal pain score (0-10 NRS on Tampon Test) as a continuous outcome variable; includes fixed effect terms for treatment (nortriptyline, lidocaine/estradiol, and their interaction), visit, treatment visit interaction, center, and fixed effect covariates vector including age, VBD subtype (binary variable where VBD-c is coded as 0 and VBD-p coded as 1), race (three levels "white", "black" and "other" race, coded into two binary dummy variables with European American serving as a reference level).

Overall treatment effect of nortriptyline, lidocaine/estradiol, and their interaction will be evaluated using an F-test. If significant ($p < 0.05$), treatment differences (each of 3 treatment groups minus placebo) in the Least-Squares means (LS means), their 2-sided 95% CIs, and associated p-

values will be estimated from the MMRM model. P-values will be compared with the significance threshold Bonferroni-corrected for 3 tests (i.e. alpha 0.0166).

To answer question 1b, we will fit a MMRM model analogous to 1a, with additional terms of VBD subtype visit interaction, treatment VBD subtype interaction, and treatment visit VBD subtype interaction. The significance of the additional interaction terms will be evaluated using a F-test comparing the full model in 1b and the reduced model in 1a. Significant ($p < 0.05$) F-test will suggest that the effect of either nortriptyline or lidocaine/estradiol cream, or both, differ by VBD subtype. In this case, we will compare the LS means of the treatment differences in each treatment-VBD-subtype subgroup, after appropriate Bonferroni correction.

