If the results for question 1a or 1b are statistically significant, the following primary outcomes will be analyzed using the same modeling strategies (models in 1a and 1b above): % decrease in pain score (tampon test) from baseline to the 16-week time point and % decrease in perceived pain on the SF-MPQ from baseline to the 16-week time point. Secondary outcomes include change in mucosal, vulvovaginal muscle, and remote bodily PPTs from baseline to the 16-week time point. Secondary outcomes also include change in pain scores and PPTs from baseline to the 8-week time point and change in pain scores and PPTs from the 16-week to the 24-week time point.

If the result for question 1b is non-significant, we will use the continuous COPC score in model 1b instead of a dichotomous VBD classification to compare treatment success for VBD-p and VBD-c. In addition, we use a binary treatment outcome (achievement of 30% pain reduction) to identify the optimal cutoff of the continuous COPC score in each treatment group.

Secondary analyses of muscle pain based on PPTs will also determine: a) the proportion of women with VBD that have a pelvic muscle pain component; b) differences in the distribution of muscle pain in VBD-p and VBD-c groups; and c) presence of muscle pain to predict treatment outcome. The latter will be tested by including the muscle pain variable (continuous or dichotomous) as part of the fixed effect term in model 1a.

Expected Outcomes. **1)** For women with VBD-p, peripheral lidocaine/estradiol treatment will be more effective than placebo or nortriptyline in reducing numeric pain ratings on the tampon test, perceived pain on the SF-MPQ, and pelvic PPTs on the algometer test at week 8 and week 16. **2)** For women with VBD-c, centrally-targeted nortriptyline treatment will be more effective than placebo or lidocaine/estradiol in reducing numeric pain ratings on the tampon test, perceived pain on the SF-MPQ, and pelvic/remote bodily PPTs on the algometer test at week 16. **3)** For women with VBD-c, combined peripheral and centrally-targeted treatments will be most effective in reducing pain on primary and secondary outcome measures at week 16. **4)** The two VBD subtypes will exhibit differential responses to treatment withdrawal at week 16, such that at the week 24 visit women with VBD-c will exhibit increases in pain after treatment withdrawal compared to women with VBD-p.

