To answer question 3b, we will fit a MMRM model analogous to 1a, with additional terms of treatment cytokine (in blood and vaginal samples) interaction, visit cytokine interaction, and treatment visit cytokine interaction. Significance of additional interaction terms will be evaluated using an F-test. Significant ($p < 0.05$) F-test will suggest that treatment effects by nortriptyline or lidocaine/estradiol cream or both, are modified by cytokines.

Secondary analyses for Aim 3 will include the association of Tier 2 biomarkers (cytokines and miRNAs) with VBD subtype and interaction with treatment response. These analyses will be analogous to those specified for questions 3a and 3b, with p-value thresholds kept at 0.05 due to exploratory nature of these analyses. In our secondary analyses we will also evaluate the change of biomarker concentrations (blood and vaginal samples) over time (at 0, 8, 16, and 24 weeks) in each treatment group and VBD subtype. We hypothesize that these biomarkers may serve as intermediate phenotypes for treatment success in VBD patient subgroups.

Expected Outcomes. 1) Women with VBD-p will have higher levels of inflammatory mediators in peripheral vaginal samples, while women with VBD-c will have higher levels of inflammatory mediators in circulating blood measured at the baseline visit (0 weeks). 2) Abnormalities in baseline vaginal cytokine and miRNA biomarkers will predict a positive response to peripheral lidocaine/estradiol treatment, while abnormalities in blood biomarkers will predict a positive response to centrally-targeted nortriptyline or combined treatment. 3) Peripheral treatment will resolve abnormalities in vaginal biomarkers evaluated at 8, 16, and 24 weeks, while central treatment will resolve abnormalities in blood biomarkers evaluated at 16 weeks.

All analyses will be performed using the Intent-to-Treat (ITT) population. The ITT population will include all randomized participants. Participants will be grouped according to their randomized allocation, regardless of whether the allocated therapy was administered or switched.

Any deviations from the statistical analyses described above, due to unforeseen circumstances, will be documented in the Statistical Analysis Plan (SAP).

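### Section 15.3 names a repeated-measures model for Aim 2 but defines its outcome as the week-16 value and cites a circular model 2b, so the primary analysis contradicts itself

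*Combined protocol and SAP*

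**What the plan says.** Section 15.3 answers question 2b (does the treatment effect on SF-12 physical health, SF-12 mental health and PROMIS sexual health differ by subtype?) as follows: "three MMRM models analogous to model 2b will be fit, where Y is a continuous variable representing the primary outcomes measured at 16 weeks". It then adds: "we will jointly evaluate the significance of additional interaction terms using an F-test".

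The only earlier model with such added terms is model 1b in section 15.2: "we will fit a MMRM model analogous to 1a, with additional terms of VBD subtype visit interaction, treatment VBD subtype interaction", plus the three-way treatment, visit and subtype interaction. Its parent, model 1a, is explicit about the outcome: "the MMRM model includes longitudinal pain score (0-10 NRS on Tampon Test) as a continuous outcome variable". Section 15.2 justifies these models as ones "which account for missing data as an integral part of the analyses under the assumption of ignorable missing".

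Section 15.2 also sends outcomes named at a single time point through models 1a and 1b, for example the percent "decrease in perceived pain on the SF-MPQ from baseline to the 16-week time point".

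Section 4 has the SF-12 and the "PROMIS questionnaire administered at 0, 8, 16, and 24 weeks", and Appendix A agrees. The end of section 15.4 places all analyses on the intent-to-treat population: "The ITT population will include all randomized participants".

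**The concern.** The sentence that defines the Aim 2 primary model contains two incompatible instructions. It asks for a mixed model for repeated measures, but the outcome it defines has one measurement per woman. The cross-reference that should settle the matter points back to itself.

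Two competent analysts could therefore fit different models. One would fit all visits and extract week 16. The other would fit week-16 scores alone, so a woman with a week-8 score but no week-16 score would contribute nothing. The two would differ in who is analysed, in the test that decides whether subgroup contrasts are examined, and, under some dropout patterns, in the estimated effect. The reason the plan gives for using repeated-measures models, their handling of missing data, would not apply to the second.

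**Working it through.** **1. Can model 1b be fitted to one visit?** Model 1a has treatment, visit and treatment-by-visit terms. Model 1b adds subtype-by-visit, treatment-by-subtype and treatment-by-visit-by-subtype. With four arms (3 df), two subtypes (1 df) and V visits (V - 1 df), the added terms have (V - 1) + 3 + 3(V - 1) degrees of freedom.

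| Outcome entered | Added df |
|---|---|
| Week 16 only (V = 1) | 0 + 3 + 0 = 3 |
| Weeks 8, 16, 24 (V = 3) | 2 + 3 + 6 = 11 |
| Weeks 0, 8, 16, 24 (V = 4) | 3 + 3 + 9 = 15 |

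With V = 1, every visit term disappears.

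**2. Who is analysed?** Section 15.6 gives 400 women and 20% attrition without its timing. If all of it occurs by week 16, 0.20 × 400 = 80 women have no week-16 score: 20 per arm on average, leaving 80 of 100.

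**3. Precision.** The documents give no SD, correlation or power for the SF-12 or PROMIS, so the only figure to reproduce is for Aim 1: 0.98 points per arm against placebo (SD 2.0, correlation 0.5, alpha 0.0167, power 0.80). The detectable difference is (2.393 + 0.842) × 2.0 × √(2/n).
- 80 completers per arm: 3.235 × 0.3162 = 1.02 points. Power at 0.98 is 0.760, so the stated figure is not reproduced.
- A four-visit model with compound symmetry, separate means by arm and visit, and 20% lost by week 16 gives an effective n of 84 to 86 per arm. The detectable difference is 0.99 to 1.00 points and power at 0.98 is 0.784 to 0.792, close to the stated 0.80.

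The Aim 1 sizing is thus compatible with a model that uses partial follow-up. The sizing formula is not stated, so this is supporting evidence only. The literal Aim 2 reading costs about 3% in detectable difference (1.023 against 0.988 to 0.997, or 0.51 against 0.49-0.50 SD).

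**4. Bias.** Dropout after week 8 and its cause are assumptions here. Suppose leaving depends only on the week-8 score. In SD units, the mean week-16 score of women who stay is then shifted by correlation × (mean standardised week-8 score of stayers), and the bias in the contrast is the difference between the two arms' shifts. Take correlation 0.5 and a logistic dropout model with an odds ratio of 2.0 or 3.3 per SD of week-8 response:

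| Assumed loss after week 8 | Stayers' week-8 mean (OR 2.0 / 3.3) | Week-16-only bias |
|---|---|---|
| 22%, dependence in one arm | 0.141 / 0.214 | 0.5 × these = 0.07 / 0.11 SD |
| 10% of those seen at week 8, dependence in one arm | 0.066 / 0.104 | 0.03 / 0.05 SD |
| 22%, OR 3.3 in one arm, 2.0 in the other | 0.214 and 0.141 | 0.5 × 0.073 = 0.04 SD |
| 22%, same dependence in both arms | equal | about 0 |

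Simulation with 100 per arm and 4,000 replicates gives the same values. With 22% loss and dependence in one arm, correlations of 0.3 to 0.7 widen the range to 0.04-0.15 SD. The sign depends on which arm loses its poor responders. A fit that uses the week-8 score has bias of about 0 in all these cases.

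For scale, Table 2 and the group sizes in section 3.2 imply SF-12 mental health SDs of 1.96 × √33 = 11.3 and 2.20 × √28 = 11.6. Taking 11.4, a bias of 0.03-0.05 SD is 0.3 to 0.6 points, and 0.07-0.11 SD is 0.8 to 1.3 points.

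**The case against.** The best defence is that this is loose drafting of a longitudinal model. The sentence itself says MMRM and calls the models analogous to an earlier one. The added interaction terms make sense only with several visits. The scores are collected at four visits, and all analyses are assigned to all randomised women. The phrase about 16 weeks is also the plan's routine endpoint label: section 12 describes the tampon-test endpoint in the same way, yet section 15.2 models that score longitudinally. The change and percent-change outcomes in section 15.2 can likewise be fitted at every visit and reported at week 16.

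This defence stands as to intent. A reader might infer that the plan has chosen a completers' comparison, but no section says so. It does not remove the fault. The only explicit definition of Y in section 15.3 is the week-16 value, the reference that should override it is circular, and the section lists week-8 change as a separate secondary outcome, which fits a model for each time point.

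A reader might also infer that the literal analysis is biased whenever leaving depends on response. That is too strong: when the dependence is the same in both arms, the contrast is essentially unbiased.

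**Conclusion.** The point holds as a contradiction within the plan that should be corrected before analysis. It affects the treatment analysis of all three Aim 2 primary outcomes. Taken literally, section 15.3 yields a model without estimable visit terms, a 3-df interaction test, and the exclusion of women without a week-16 score, contrary to the all-randomised population in section 15.4.

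The loss of precision is small. The bias ranges from about 0 to 0.11 SD at correlation 0.5. The upper end requires about 22% loss after week 8 with response-dependent dropout in one arm only. The documents state neither the timing nor the mechanism of attrition, so no single value is the expected one. The degrees of freedom need no such assumption; the count of 80 excluded women is an upper limit that assumes all attrition occurs by week 16.

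**What to change.** In section 15.3:
- Define Y as the score at each scheduled visit (0, 8, 16 and 24 weeks) and replace both references to model 2b with model 1b.
- Name the week-16 treatment contrast as the primary result, and list the terms and degrees of freedom of the joint interaction test.
- Enter baseline as an outcome visit. With weeks 8, 16 and 24 alone, a woman lost before week 8 would still contribute nothing. Model 1a lists no baseline score among its covariates, so the role of baseline has to be stated in any case.

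In section 15.2, state that change and percent-change outcomes sent through models 1a and 1b are modelled at all visits, with the contrast at the named time point extracted.

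The cost is wording only. Appendix A already schedules the SF-12 and PROMIS at all four visits.

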5 BASIC STUDY DESIGN

Vestibulodynia UPDATE is a multi-center, randomized, double-blind, placebo-controlled trial designed to determine the efficacy of peripheral lidocaine/estradiol cream, centrally-targeted nortriptyline pills, and combined treatments compared to matching placebo with the primary endpoints of change in pain, self-reported health, and cytokine/microRNA measures at 16 weeks and secondary endpoints of change in these measures at 8 weeks and 24 weeks.

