12 OUTCOME DETERMINATIONS

Aim 1. Determine the efficacy of peripheral, central, and combined treatments in alleviating pain among women with VBD-p and VBD-c.

Primary Endpoints:

- Ia. pain score during tampon test at 16 weeks
- Ib. self-reported pain *via* SF-MPQ at 16 weeks

Secondary Endpoints:

- Ila. experimental pain *via* local and remote PPTs at 16 weeks
- Ilb. COPC pain levels *via* COPC follow-up survey at 16 weeks
- Ilc. Pain scores and PPTs at 8 weeks and 24 weeks

Aim 2. Determine the efficacy of peripheral, central, and combined treatments in improving patient reported outcomes among women with VBD-p and VBD-c.

Primary Endpoints:

- Ia. self-reported physical/mental health *via* SF12v2 at 16 weeks
- Ib. sexual health *via* PROMIS at 16 weeks

Secondary Endpoints:

- Ila. mood *via* SCL-27 at 16 weeks
- Ilb. somatic awareness *via* PILL at 16 weeks
- Ilc. perceived stress *via* PSS at 16 weeks
- Ild. sleep *via* sleep scale at 16 weeks
- Ile. Patient reported outcomes at 8 weeks and 24 weeks

Aim 3. Determine the efficacy of peripheral, central, and combined treatments in normalizing cytokine and microRNA expression profiles in vaginal and blood tissues collected from women with VBD-p and VBD-c.

Primary Endpoints:

- Ia. cytokine levels *via* mesoscale discovery assays at 16 weeks
- Ib. microRNA levels *via* sequencing read at 16 weeks

Secondary Endpoints:

- Ila. cytokine and microRNA levels at 8 weeks and 24 weeks
- Ilb. Aim 3 will also identify cytokine and microRNA biomarkers at baseline that predict treatment response at 8, 16, and 24 weeks

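### Aim 2 promises efficacy on patient-reported outcomes against placebo, but Section 15.3 plans no overall treatment test and no active-versus-placebo contrast for its primary scores

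*Combined protocol and SAP*

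**What the plan says.** Section 12 (Outcome Determinations) words the aim as: "Determine the efficacy of peripheral, central, and combined treatments in improving patient reported outcomes among women with VBD-p and VBD-c". Section 5 (Basic Study Design) sets the treatments "compared to matching placebo with the primary endpoints of change in pain, self-reported health, and cytokine/microRNA measures at 16 weeks". The expected outcomes at the end of Section 15.3 predict superiority over placebo as well as over the other active treatment.

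Section 15.3 then poses two primary questions.

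- **2a:** "At baseline, do women with VBD-c exhibit worse perceived physical, mental, or sexual health than women with VBD-p". This is a baseline regression with no treatment term, tested at 0.0166 for each of three scores.
- **2b:** "is peripheral treatment with lidocaine/estradiol cream more effective than nortriptyline in VBD-p, and central treatment with nortriptyline more effective than lidocaine/estradiol cream in VBD-c". Placebo is not named.

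For 2b, "three MMRM models analogous to model 2b will be fit", and "we will jointly evaluate the significance of additional interaction terms using an F-test". The next step depends on that test being significant: "In this case, we will compare the LS means of the treatment differences in each treatment-VBD-subtype subgroup", after a Bonferroni correction that is not spelled out.

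Section 15.2 (Aim 1) is built differently. Model 1a has an overall treatment F-test and then three active-minus-placebo contrasts at 0.0166, and neither step depends on subtype. Model 1b adds the subtype interactions. Section 15.2 carries models 1a and 1b over to further pain outcomes only.

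**The concern.** Section 15.3 has a counterpart to model 1b and none to model 1a. A benefit that is similar in both subtypes is a plausible and favourable result, and it is the case in which a subtype-interaction test has nothing to find. The analyst following the plan would then report a non-significant interaction and stop. No planned result would say whether any treatment improved SF-12 or PROMIS scores relative to placebo, although these are primary endpoints. A treatment test chosen after that point would be post hoc. Aim 1 at least has a stated fallback when 1b is non-significant (the continuous COPC score). Section 15.3 states none.

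**Working it through.** **1. Which planned step tests efficacy?**

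| Step | Aim 1 (15.2) | Aim 2 (15.3) |
|---|---|---|
| Overall treatment F-test | Yes, model 1a, at 0.05 | None |
| Each active arm minus placebo | Yes, three contrasts at 0.0166 | None stated |
| Subtype-interaction F-test | Yes, model 1b, at 0.05 | Yes, 2b, alpha not stated |
| Treatment differences by subtype | If 1b is significant | If 2b is significant |

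The reference to model 2b inside 2b points to itself. By content it must mean model 1b. That reading keeps the condition, because 1b carries it too. I take the alpha from 1b: "Significant ($p < 0.05$) F-test will suggest".

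**2. How often is the condition met under a shared benefit?** There are two readings.

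(a) *Week 16 only, or parallel subtype courses.* The treatment-by-subtype null is true, so the F-test rejects at its error rate, nominally 5%. A simulation of the 3-df test (80 per arm, 4,000 runs per setting, shared benefit of 0.3 or 0.5 SD, subtype splits 40/60 and 50/50) gave 4.8% to 5.5%.

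(b) *All visits, as model 1b is written.* The added terms are subtype-by-visit, treatment-by-subtype and treatment-by-visit-by-subtype. With four arms and three post-baseline visits this is 2 + 3 + 6 = 11 df. The subtype-by-visit part contains no treatment. Suppose the subtypes differ by δ SD at week 24 only, with identical treatment effects. Take N = 320, a 60/40 split and within-subject correlation 0.5 (Section 15.6). Then the noncentrality is

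320 × 0.6 × 0.4 × (2/3)δ² / (1 − 0.5) = 102.4δ².

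| δ (assumed) | Noncentrality | F-test significant |
|---|---|---|
| 0.2 | 4.10 | 21% |
| 0.3 | 9.22 | 48% |
| 0.4 | 16.38 | 79% |

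**3. The plan's own power figures.** Section 15.6 gives none for an Aim 2 treatment comparison. For the tampon test it states 80% power for 0.82 (overall, alpha 0.05) and 0.98 (one arm versus placebo, alpha 0.0167). The SD of change is 2.0 × √(2 × (1 − 0.5)) = 2.0. With 80 per arm, power is 76% for both. With 86.7 per arm (assuming the 20% attrition accrues evenly to week 24, so 13.3% by week 16) it is 80% for both. With 100 per arm it is 86%. The stated figures therefore reproduce at about 87 per arm.

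**4. What an unconditional test would offer.** Inputs: 400 women less 20% = 320, so 80 per arm (Section 15.6 itself uses 320 in its cytokine calculation), and the same benefit of d SD in all three active arms. The values of d are assumed, because the documents give no target for SF-12 or PROMIS.

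- Overall 3-df F-test: noncentrality = 80 × (3/4) × d².
- One active-versus-placebo contrast: two-sided t-test, noncentrality = d × √(80/2) = 6.325d, ignoring the preceding overall test.
- Alphas: 0.05/3 = 0.0167 and 0.0167/3 = 0.0056.

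| d | Overall F at 0.0167 | One contrast at 0.0167 | One contrast at 0.0056 |
|---|---|---|---|
| 0.3 | 30% | 30% | 18% |
| 0.4 | 58% | 55% | 39% |
| 0.5 | 82% | 77% | 64% |
| 0.6 | 95% | 91% | 84% |

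With 86.7 per arm the overall test rises to about 33%, 63%, 86% and 97%.

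**The case against.** The best defence is that Aim 2 is deliberately about subtypes. The hypotheses in Section 4 are differential, and 2b tests them. This stands as a reason to keep 2b. It does not account for the aim, the comparator and the expected outcomes, all of which also claim efficacy.

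A second defence is that the models for 2b are fitted unconditionally and include treatment terms. If 2b follows 1b, the F-test even compares the full model with a reduced model of type 1a, so that model would be fitted to each score. A reader might therefore go too far in inferring that no treatment estimate would exist. One could be extracted, but the plan gives it no test, contrast or alpha.

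A third is that the condition need not fail. A reader might infer that a shared benefit could never reach a treatment comparison, or that the chance is 5% whatever happens. The documents do not support either statement without qualification. The joint test includes subtype-by-visit terms, and Section 15.3 itself expects the subtypes to diverge between weeks 16 and 24. However, significance through those terms says only that the subtypes follow different courses. Even the comparisons that follow need not include placebo, which enters only if treatment differences are read as model 1a defines them.

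Last, Section 15.4 lets deviations be documented in the SAP when circumstances are unforeseen. A shared benefit is foreseeable.

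**Conclusion.** The concern holds as a structural gap. Section 15.3 has no planned efficacy test for the three Aim 2 primary scores that does not depend first on a significant subtype-interaction test. The conclusion follows from the text and rests on none of the assumed effect sizes.

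Its size depends on the reading. Under a shared benefit, treatment comparisons follow in about 5% of trials if subtype courses are parallel or only week 16 is tested. The share is higher if courses diverge: 21% to 79% for an assumed week-24 difference of 0.2 to 0.4 SD. Neither figure is power to show efficacy. An unconditional overall test would have roughly 30% to 95% power over assumed effects of 0.3 to 0.6 SD with 320 completers.

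**What to change.** Add a primary question to Section 15.3, to be answered whatever the subtype test shows:

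1. Fit model 1a to SF-12 physical, SF-12 mental and PROMIS sexual health.
2. Test the overall treatment effect at 16 weeks at 0.0167 per outcome, the three-outcome correction that 2a already uses.
3. If significant, compare each active arm with placebo at a prespecified alpha. One option is 0.0167/3 = 0.0056 within each outcome, which follows model 1a's Bonferroni rule and covers all nine contrasts.

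Keep 2b as a separate effect-modification question. Correct its self-reference to model 1b, state the alpha of its F-test, and say whether the subtype-by-visit terms belong in it.

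The cost is plan wording, three more model fits on data already being collected, and a stricter alpha per contrast: at 0.5 SD, power for one contrast is 64% at 0.0056 against 77% at 0.0167. The change should be made before unblinding.
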